6.4. RETESTS, UNSCHEDULED VISITS AND EARLY TERMINATION DATA

In general, for by-visit summaries, data recorded at the nominal visit will be presented.

Unscheduled measurements will not be included in by-visit summaries but will contribute to the best/worst case value where required (e.g. shift tables).

Treatment Early termination data will not be included in by-visit summaries.

In the case of a retest (same visit number assigned), the earliest available measurement for that visit will be used for by-visit summaries.

Listings will include scheduled, unscheduled, retest and early discontinuation data.

Document:	K:\AAA\Ga-PSMA-R2\VYA27826\ Biostatistics\Documentation\SAP\v2.0\Ga-PSMA-R2-SAP_v2.0
Author:	[Redacted] Version Number: 2.0
	Version Date: 29JUN2020
Template No.:	CS_TP_BS016 Revision 5
Effective Date:	01Apr2018 Reference: CS_WI_BS005

6.5. WINDOWING CONVENTIONS

No visit windowing will be performed for this study.

6.6. STATISTICAL TESTS

There will be no formal statistical testing of data.

6.7. COMMON CALCULATIONS

For quantitative measurements, change from baseline will be calculated as:

- Test Value at Visit X – Baseline Value

For quantitative measurements, percentage of change from baseline will be calculated as:

$$\left(\frac{\text{Test Value at Visit X} - \text{Baseline Value}}{\text{Baseline Value}} \right) \times 100$$

6.8. SOFTWARE VERSION

All analyses will be conducted using SAS version 9.4 or higher.

7. STATISTICAL CONSIDERATIONS

7.1. ADJUSTMENTS FOR COVARIATES AND FACTORS TO BE INCLUDED IN ANALYSES

There will be no statistical testing for safety data, and no covariate adjustment.

7.2. MULTICENTER STUDIES

The study will be conducted at approximately 4 sites in the US. All data will be pooled for summaries of safety with no summaries presented by center.

Document:	K:\AAA\Ga-PSMA-R2\VYA27826\ Biostatistics\Documentation\SAP\v2.0\Ga-PSMA-R2-SAP_v2.0
Author:	[Redacted] Version Number: 2.0

Template No.: CS_TP_BS016 Revision 5
Effective Date: 01Apr2018

Version Date: 29JUN2020
Reference: CS_WI_BS005

7.3. MISSING DATA

Missing safety data will not be imputed.

Missing severity and relatedness of AEs will be handled as described in sections 14.1.1.1 and 14.1.1.2 of this analysis plan.

7.4. MULTIPLE COMPARISONS/ MULTIPLICITY

Not applicable.

7.5. EXAMINATION OF SUBGROUPS

No subgroup analyses will be performed for this study.

8. OUTPUT PRESENTATIONS

APPENDIX 1 shows conventions for presentation of data in outputs.

The templates provided with this SAP describe the presentations for this study and therefore the format and content of the summary tables, figures and listings to be provided by [REDACTED] Biostatistics.

9. DISPOSITION AND WITHDRAWALS

All patients who provide informed consent will be accounted for in this study.

The counts of the analysis sets will be presented:

- All Patients Enrolled Set (ENR)
- Full Analysis Set (FAS)
- Per Protocol Set (PPS)

The following patient disposition and withdrawals will be presented for the ENR set:

- Screened
- Screen failures
- Phase I
- Phase II

Document:	K:\AAA\Ga-PSMA-R2\VYA27826\ Biostatistics\Documentation\SAP\v2.0\Ga-PSMA-R2-SAP_v2.0		
Author:	[REDACTED]	Version Number:	2.0
Template No.:	CS_TP_BS016 Revision 5	Version Date:	29JUN2020
Effective Date:	01Apr2018	Reference:	CS_WI_BS005

Statistical Analysis Plan

- Number of patients receiving study medication
- Completed study imaging assessments (assessed at Day 1)
- Discontinued from study, reason for premature discontinuation from study

Duration of follow-up will be presented for the ENR set. Duration of follow-up (day) is defined as date of completion/discontinuation - date of first administration + 1.

Critical and major protocol deviations (as defined in section 5.3) will be presented for the ENR set.

10. DEMOGRAPHIC AND OTHER BASELINE CHARACTERISTICS

Demographic data and other baseline characteristics will be presented for the FAS and PPS.

No statistical testing will be carried out for demographic or other baseline characteristics.

The following demographic characteristics will be reported:

- Age (years)
- Race (American Indian or Alaska Native, Asian, Black or African American, Native Hawaiian or Other Pacific Islanders, White, Other)
- Ethnicity (Hispanic or Latino, Not Hispanic or Latino, Not Reported, Unknown)
- Weight (kg)
- Height (cm)

The following baseline characteristics will be reported:

- ECOG performance status at baseline (0, ≥1)
- PSA test (ng/mL)

11. MEDICAL AND PROSTATE CANCER HISTORY

Medical and prostate cancer history information will be presented for the FAS and PPS and will be coded using MedDRA version 21.0 or higher.

All reported medical and prostate cancer history will be listed.

Document: K:\AAA\Ga-PSMA-R2\VYA27826\ Biostatistics\Documentation\SAP\v2.0\Ga-PSMA-R2-SAP_v2.0
 Author: [Redacted] Version Number: 2.0
 Version Date: 29JUN2020
 Template No.: CS_TP_BS016 Revision 5 Reference: CS_WI_BS005
 Effective Date: 01Apr2018

11.1. MEDICAL HISTORY

Medical history will be presented by System Organ Class (SOC) and (Preferred Term (PT)). They will be sorted by decreasing frequency for SOC and for PT within SOC, based on total count. See APPENDIX 2 for handling of partial dates for medical history.

11.2. PROSTATE CANCER HISTORY

The following prostate cancer history information, as reported in the eCRF, will be summarized:

- Time since first prostate cancer diagnosis (months)
- Time since first metastasis (months)
- Time since disease progression (months)
- Number of PSMA positive patients
- Number of patients by initial diagnostic stage (IA, IB, IIA, IIB, IIIA, IIIB, IIIC, IV, unknown)
- Number of patients by current diagnostic stage (IA, IB, IIA, IIB, IIIA, IIIB, IIIC, IV, unknown)
- Number of patients by castration type (surgery, pharmacological, not applicable)
- Number of patients by primary and secondary Gleason score:
 - Primary Gleason score=3 and Secondary Gleason score=3
 - Primary Gleason score=3 and Secondary Gleason score=4
 - Primary Gleason score=4 and Secondary Gleason score=3
 - Primary Gleason score=4 and Secondary Gleason score=4
 - Primary Gleason score=4 and Secondary Gleason score=5
 - Primary Gleason score=5 and Secondary Gleason score=4
 - Primary Gleason score=5 and Secondary Gleason score=5
- Number of patients by Total Gleason score ≥ 6 (6, 7, 8, 9, 10)

Document: K:\AAA\Ga-PSMA-R2\VYA27826\ Biostatistics\Documentation\SAP\v2.0\Ga-PSMA-R2-SAP_v2.0
 Author:  Version Number: 2.0

Version Date: 29JUN2020

Template No.: CS_TP_BS016 Revision 5
 Effective Date: 01Apr2018

Reference: CS_WI_BS005

11.2.1. DERIVATIONS

- Time since first prostate cancer diagnosis (months) = (date of screening – date of first prostate cancer diagnosis + 1) / 30.4375
- Time since first metastasis (months) = (date of screening - date of first metastasis + 1) / 30.4375
- Time since disease progression (months) = (date of screening – date of disease progression + 1) / 30.4375

See APPENDIX 2 for handling of partial dates for prostate cancer history.

12. CANCER THERAPIES, MEDICATIONS, PROCEDURES AND RADIOTHERAPY

12.1. PRIOR AND CONCOMITANT CANCER THERAPIES

Prior and concomitant cancer therapies, as reported in the “Prior and Concomitant Cancer Therapy Medications” eCRF page, will be presented for the FAS and PPS using WHO-DD Preferred Names.

- Prior cancer therapies are those which started prior to the day of first and single dose of study medication.
- Concomitant cancer therapies are those which:
 - started prior to, on or after the first and single dose of study medication, AND
 - ended on or after the date of first and single dose of study medication or were ongoing at the end of the study.

Number of patients with at least one Line of therapy (Neoadjuvant, Adjuvant, Therapeutic for Metastatic Disease, Unknown), number of patients with at least one Therapy type (Chemotherapy, Hormonal, Biological, Immunotherapy, Other), number of patients with at least one Treatment intent (Curative, Palliative, Diagnostic, Salvage, Other) will be presented as well as the medication and the best response of the latest therapy the patient received (Complete response, partial response, stable disease, progressive disease, not evaluable).

12.2. PRIOR AND CONCOMITANT NON-CANCER MEDICATIONS

Medications will be presented for the FAS and PPS and coded using WHO Drug Dictionary version MAR2018 or higher if available at the time of the Database Lock. The medications will be summarized by WHO-DD Preferred Names, sorted by decreasing frequency based on total count.

Document:	K:\AAA\Ga-PSMA-R2\VYA27826\ Biostatistics\Documentation\SAP\v2.0\Ga-PSMA-R2-SAP_v2.0
Author:	 Version Number: 2.0

Template No.: CS_TP_BS016 Revision 5
 Effective Date: 01Apr2018

Version Date: 29JUN2020

Reference: CS_WI_BS005

See APPENDIX 2 for handling of partial dates for medications, in the case where it is not possible to define a medication as prior or concomitant, the medication will be classified by the worst case; i.e. concomitant.

- Prior medications are those which started prior to the day of first and single dose of study medication.
- Concomitant medications are those which:
 - started prior to, on or after the first and single dose of study medication,
AND
 - ended on or after the date of first and single dose of study medication or were ongoing at the end of the study.

All prior and concomitant prohibited/restricted medications outlined in protocol section 5.6, as determined by the medical advisor, will be listed.

12.3. PRIOR AND CONCOMITANT PROCEDURES

Prior and Concomitant Procedures (procedure, surgery or non-drug therapy) will be presented by SOC and PT. They will be sorted by decreasing frequency for SOC and for PT within SOC based on total count. See APPENDIX 2 for handling of partial dates for prior and concomitant procedures. In the case where it will not be possible to define a procedure as previous or active/concomitant.

- Prior procedures are defined as those which started prior to the first and single dose of study medication.
- Concomitant procedures are defined as those which:
 - started prior to the first and single dose of study medication and are ongoing or active at the date of the first and single dose of study medication
OR
 - started on or after the first and single dose of study medication.

12.4. PRIOR AND CONCOMITANT RADIOTHERAPY

Prior and concomitant radiotherapy, using radiation type as reported in the eCRF, will be presented by radiation type and treatment intent. The total dose received (Gray) will also be summarized. See APPENDIX 2 for handling of partial dates for prior and concomitant radiotherapies. In the case where it will not be possible to define a radiotherapy as previous or active/concomitant.

- Prior radiotherapies are defined as those which started prior to the first and single dose of study medication.
- Concomitant radiotherapies are defined as those which:
 - started prior to the first and single dose of study medication and are ongoing or active at the date of the first and single dose of study medication
OR
 - started on or after the first and single dose of study medication.

13. STUDY MEDICATION EXPOSURE

The following exposure information, as reported in the "68Ga-PSMA-R2 Injection" page of the eCRF, will be

Document:	K:\AAA\Ga-PSMA-R2\VYA27826\ Biostatistics\Documentation\SAP\v2.0\Ga-PSMA-R2-SAP_v2.0
Author:	 Version Number: 2.0

Version Date: 29JUN2020

Template No.: CS_TP_BS016 Revision 5
 Effective Date: 01Apr2018

Reference: CS_WI_BS005

summarized for the FAS and PPS:

- pH
- Radiochemical Purity (%)
- Pre-injection total dose in syringe (MBq)
- Post-injection residual dose in syringe (MBq)
- Total dose injected (MBq)
- Pre-injection volume of solution (mL)
- Post-injection volume of solution (mL)
- Volume of solution administrated (mL)
- Gamma counter calibration factor
- Appearance (Clear and Colourless / Not Clear and Colourless)
- Number of patients with injection interrupted
- Reason for injection interruption

14. SAFETY OUTCOMES

All outputs for safety outcomes will be based on the FAS. Safety will be assessed as the primary objective in this study.

The primary endpoints are defined as:

- Adverse events and serious adverse events (SAEs)
- Absolute changes and changes from baseline in clinical laboratory parameters, vital signs and electrocardiogram (ECG)

14.1. ADVERSE EVENTS

Adverse Events will be coded using the MedDRA central coding dictionary, Version 21.0 or higher.

They will be sorted by decreasing frequency for SOC and for PT within SOC, based on total count.

Treatment emergent adverse events (TEAEs) are defined as AEs that started or worsened in severity on or after the first and single dose of study medication and until the last actual follow up visit.

Document:	K:\AAA\Ga-PSMA-R2\VYA27826\ Biostatistics\Documentation\SAP\2.0\Ga-PSMA-R2-SAP_v2.0
Author:	 Version Number: 2.0

Template No.: CS_TP_BS016 Revision 5
 Effective Date: 01Apr2018

Version Date: 29JUN2020
 Reference: CS_WI_BS005

See Appendix 2 for handling of partial dates for AEs. In the case where it is not possible to define an AE as treatment emergent or not, the AE will be classified by the worst case; i.e. treatment emergent.

An overall summary of number of patients within each of the categories described in the sub-sections below, will be provided as specified in the templates.

Listings will include TEAEs and Non-TEAEs.

14.1.1. ALL TEAEs

Incidence of TEAEs, and number of events, will be presented by SOC and PT and broken down further by maximum severity and relationship to study medication and study procedure.

14.1.1.1. Severity

Severity is classed as mild, moderate, severe, life threatening/disabling or death. TEAEs starting after the first dose of study medication with a missing severity will be classified as severe. If a patient reports a TEAE more than once within that SOC/ PT, the AE with the worst-case severity will be used in the corresponding severity summaries.

14.1.1.2. Relationship to Study Medication

A related TEAE is defined as a TEAE with a relationship to study medication as "Reasonable possibility" according to the investigator. TEAEs with a missing relationship to study medication will be regarded as related to study medication. If a patient reports the same AE more than once within that SOC/ PT, the AE with the worst-case relationship to study medication will be used in the corresponding relationship summaries.

14.1.1.3. Relationship to Study Procedure

A related TEAE is defined as a TEAE with a relationship to study procedure as "Reasonable possibility" according to the investigator. TEAEs with a missing relationship to study procedure will be regarded as related to study procedure. If a patient reports the same AE more than once within that SOC/ PT, the AE with the worst-case relationship to study procedure will be used in the corresponding relationship summaries.

14.1.2. TEAEs LEADING TO DISCONTINUATION OF STUDY

TEAEs leading to study discontinuation will be identified by using the "Caused Study Discontinuation" category on the AE page of the eCRF.

For TEAEs leading to study discontinuation, a summary by SOC and PT will be prepared.

AEs leading to study discontinuation will be listed.

14.1.3. SERIOUS ADVERSE EVENTS

Serious adverse events (SAEs) are those events recorded as "Serious" on the Adverse Events page of the (e)CRF.

Document:	K:\AAA\Ga-PSMA-R2\VYA27826\ Biostatistics\Documentation\SAP\v2.0\Ga-PSMA-R2-SAP_v2.0
Author:	[Redacted] Version Number: 2.0
Version Date:	29JUN2020
Template No.:	CS_TP_BS016 Revision 5
Effective Date:	01Apr2018
Reference:	CS_WI_BS005

A summary of serious TEAEs by SOC and PT will be prepared.

Serious AEs will be listed.

14.1.4. ADVERSE EVENTS LEADING TO DEATH

TEAEs leading to Death are those events which are recorded as "Fatal" on the Adverse Events page of the (e)CRF. A summary of TEAEs leading to death by SOC and PT will be prepared.

AEs leading to Death will be listed.

14.2. LABORATORY EVALUATIONS

Results from the local laboratory will be included in the reporting of this study for Hematology, Blood Chemistry and Urinalysis. A list of laboratory assessments to be included in the outputs, and a severity grading system is included in APPENDIX 3.

Presentations will use SI Units.

Quantitative laboratory measurements reported as "< X", i.e. below the lower limit of quantification (BLQ), or "> X", i.e. above the upper limit of quantification (ULQ), will be converted to X for the purpose of quantitative summaries, but will be presented as recorded, i.e. as "< X" or "> X" in the listings.

The following summaries will be provided for laboratory data:

- Observed values and change from baseline by visit (for quantitative measurements)
- Summary of qualitative clinical laboratory evaluations by visit
- Incidence of abnormal values at any time post-baseline according to normal range criteria
- Shift from baseline according to normal range criteria (for quantitative measurements and categorical measurements), by visit
- Shift from baseline to worst post-baseline value, according to severity grading system
- Summary of markedly abnormal post-baseline values
- Listing of patients with Grade 3 or above severity grades
- Box plots of absolute values over time and changes from baseline over time

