6.5.3. Clinical Laboratory Assessments

Clinical laboratory assessments for safety monitoring will be performed by an accredited local laboratory. Blood and urine samples for hematology, serum chemistry and urinalysis, will be prepared using standard procedures.

PSA sample will be collected at Screening (unless performed within one month of enrollment and results are available), and results will be entered into the eCRF.

The following laboratory tests will be performed at Screening, Day 1 (after the administration of the IP), Day 7, and Day 28:

- Hematology: White blood cell (WBC) count with differential, red blood cell (RBC) count, Hb, hematocrit, platelet count, mean corpuscular volume (MCV).
- Blood chemistry profile: albumin, alkaline phosphatase (AP), alanine transaminase (ALAT), aspartate transaminase (ASAT), blood urea nitrogen (BUN), corrected calcium, chloride, creatinine, eGFR (preferably CKD-EPI), glucose, uric acid, gamma-glutamyl transpeptidase (GGT), lactate dehydrogenase (LDH), potassium, sodium, total bilirubin and total protein.
- Urinalysis: (dipstick), appearance, color, pH, specific gravity, protein, glucose and occult blood, RBC and WBC counts, Casts per low power field (Casts/lpf), Protein (dipstick test accepted).

Table 2 summarizes general laboratory assessments to be performed.

Hematology	Blood Chemistry	Urinalysis [*]
• WBC with differential	• BUN	• Appearance
• RBC	• Serum creatinine	• Color
• Platelets	• eGFR	• pH
• Hb	• Albumin	• Specific gravity
• MCV	• Total bilirubin	• Glucose
• Hematocrit	• AP	• Occult blood
• PSA (Screening visit only)	• AST/ASAT	• RBC/hpf
	• ALT/ALAT	• WBC/hpf
	• Gamma-GT	• Casts/lpf
	• Sodium	• Protein (dipstick test accepted)
	• Potassium	
	• Chloride	
	• LDH	
	Corrected Calcium	
	• Glucose	
	• Total protein	
	• Uric acid	

 Table 2
 Summary of Laboratory Assessments

*A urine sample will be collected at each visit and analyzed at the clinical site if dipstick results are abnormal. WBC = white blood cell; RBC = red blood cell; Hb = hemoglobin; MCV = mean corpuscular volume; PSA = prostate specific antigen; BUN = blood urea nitrogen; eGFR = estimated glomerular filtration rate; AST/ASAT = aspartate aminotransferase; ALT/ALAT = alanine aminotransferase; gamma-GT = gamma glutamyl transferase; LDH = lactate dehydrogenase; pH = potential of hydrogen; hpf = high power field; lpf = low power field.

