14.2.2. SEVERITY GRADING FOR LABORATORY DATA

Laboratory results will be classified according to

- *The Toxicity Grading Scale for Healthy Adult and Adolescent Volunteers Enrolled in Preventive Vaccine Clinical Study.*
- *The Common Terminology Criteria for Adverse Events (CTCAE) Version 4.03*
- *The University of Delaware Criteria*

The "Grade 0" will be introduced to indicate that a certain laboratory value can be seen as "normal" and does not fulfill the criteria of severity grading either within the reference range or elevated in the other direction than defined in the APPENDIX 3.

Parameters flagged as "Medical Advisor Input Needed" in APPENDIX 3, will be graded as per medical advisor identification based on listings provided .

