eGFR (Any eGFR value > 90 will be classified as Grade 0)		b	$\leq 90 - > 60 \text{ ml/min/1.73 m}^2$	$\leq 60 - > 30 \text{ ml/min/1.73 m}^2$	$\leq 30 - > 15 \text{ ml/min/1.73 m}^2$	$\leq 15 \text{ ml/min/1.73 m}^2$
LDH		d	NA	NA	NA	NA

Document: K:\AAA\Ga-PSMA-R2\VYA27826\Biostatistics\Documentation\SAP\v2.0\Ga-PSMA-R2-SAP
 Author: [Redacted]

Template No.: CS_TP_BS016 Revision 5
 Effective Date: 01Apr2018

Statistical Analysis Plan

Laboratory parameter		Grading Scale	a) Gradable with Toxicity Grading Scale for Healthy Adult and Adolescent Volunteers Enrolled in Preventive Vaccine Clinical Study b) Gradable with Common Terminology Criteria for Adverse Events Version 4.03 c) Gradable with University of Delaware Criteria (http://www1.udel.edu/mls/mclane/KMS3RR.html) d) Not Gradable				
			Grade 1	Grade 2	Grade 3	Markedly Abnormal	
Corrected Calcium	Hypercalcemia	a	>=2.625 - <2.75 mmol/L	>=2.75 - <2.875 mmol/L	>=2.875 - <3 mmol/L	>= 3 mmol/L	
	Hypocalcemia	a	>=2 - <2.1 mmol/L	>=1.875 - <2 mmol/L	>=1.75 - <1.875 mmol/L	<1.75 mmol/L	
Serum creatinine		a	>=132.6 - < 150.28 umol/L	>=150.28 - <176.8 umol/L	>=176.8 - <221 umol/L	>= 221 umol/L requires recheck	
Sodium	Hypernatremia	a	>=144 - <145 mmol/L	>=145 - <147 mmol/L	>=147 - <150 mmol/L	>=150 mmol/L	
	Hyponatremia	a	>=132 - <134 mmol/L	>=130 - <132 mmol/L	>=125 - <130 mmol/L	<125 mmol/L	
Potassium	Hyperkalemia	a	>=5.1 - <5.2 mmol/L	>=5.2 - <5.4 mmol/L	>=5.4 - <5.6 mmol/L	>= 5.6 mmol/L	
	Hypokalemia	a	>=3.5 - <3.6 mmol/L	>=3.3 - <3.5 mmol/L	>=3.1 - <3.3 mmol/L	< 3.1 mmol/L	
Uric acid		b	>ULN - 10 mg/dL (0.59 mmol/L) without physiologic consequences	NA	>ULN - 10 mg/dL (0.59 mmol/L) with physiologic consequences	>10 mg mmol/L	
Chloride		d	NA	NA	NA	NA	
Hematology							
RBC		d	NA	NA	NA	NA	
White blood cells with differential	WBC	Increased	a	>=10.8 - <15 10 ⁹ /L	>=15 - <20 10 ⁹ /L	>=20 - <25 10 ⁹ /L	>= 25 10 ⁹ /L
		Decreased	a	>2.5 - <=3.5 10 ⁹ /L	>1.5 - <=2.5 10 ⁹ /L	>1 - <=1.5 10 ⁹ /L	<= 1 10 ⁹ /L
	Monocytes		d	NA	NA	NA	NA
	Eosinophils		a	>=0.65 - <1.5 10 ⁹ /L	>=1.5 - <5 10 ⁹ /L	>=5 10 ⁹ /L	Hyperleukocytosis

Document: K:\AAA\Ga-PSMA-R2\VYA27826\Biostatistics\Documentation\SAP\v2.0\Ga-PSMA-R2-SAP_...
 Author: [Redacted]

Template No.: CS_TP_BS016 Revision 5
 Effective Date: 01Apr2018

Statistical Analysis Plan

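### SAP 14.2 summarizes an eGFR reported as >60 as 60, which understates a later fall and, if the converted value is graded, hides a move into Grade 2

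*SAP*

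**What the plan says.** SAP 14.2 covers quantitative results that carry a less-than or greater-than sign because they lie outside the quantifiable range. Such a result "will be converted to X for the purpose of quantitative summaries, but will be presented as recorded" in the listings. No other rule in the main SAP deals with results of this kind. The same section plans change from baseline by visit, a shift table from baseline grade to worst later grade, and a listing of Grade 3 and higher results.

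SAP 14.2.2 names the grading systems but does not say whether the value graded is the reported or the converted one. It keeps Grade 0 for a value regarded as normal: one that "does not fulfill the criteria of severity grading either within the reference range" or that deviates in the direction that is not graded.

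Appendix 3 grades eGFR (mL/min/1.73 m²) in bands closed at the upper edge. Grade 1 runs from 90 down to just above 60, Grade 2 from 60 to just above 30, Grade 3 from 30 to just above 15, and Grade 4 is 15 or lower. A note in the row adds: "Any eGFR value > 90 will be classified as Grade 0".

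Protocol 6.5.3 has eGFR and serum creatinine measured by local laboratories at Screening, Day 1, Day 7 and Day 28. CKD-EPI is preferred for eGFR but not required.

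For dipstick protein and glucose, Appendix 3 assigns trace, 1+ and 2+ to Grades 1, 2 and 3, as the scale in Protocol 11.2 does. That scale defines Grade 4 by hospitalization (or dialysis, for protein), not by a dipstick reading.

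**The concern.** Setting >X to X does little damage when high values are the harmful direction, because the result still sits at the high end. For eGFR it works the other way. It moves an adequate result down to the lowest value compatible with it, towards the graded range. A baseline treated in this way leaves less room for a later fall to show.

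This touches a primary endpoint. Protocol 2.2.1 names changes from baseline in laboratory parameters, including shifts to abnormal values, and SAP 14 repeats the change-from-baseline part. The kidney is one of the normal tissues that Protocol 1.1 lists as expressing PSMA with possible off-target effects, and it is in the dosimetry list in SAP Appendix 5. The groups are small, so one misgraded patient is 1/6 = 17% of Phase 1 or 1/12 = 8% of a Phase 2 group.

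The dipstick gap is a separate fault in the same appendix. A reading heavier than 2+ meets no listed grade by its dipstick value.

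**Working it through.** **Inputs.** The conversion rule comes from SAP 14.2 and the eGFR bands from Appendix 3. The patient values below are assumed for illustration. The plan gives no figure of its own on this point to reproduce.

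**Change from baseline.** This step needs no assumption about grading. Let the true baseline be B, above 60 and reported as >60, and let the later value P be reported as a number of 60 or less.

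- Change shown = P - 60.
- True change = P - B.
- Understatement = (P - 60) - (P - B) = B - 60.

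For B = 86 and P = 45, the change shown is 45 - 60 = -15 and the true change is 45 - 86 = -41. The understatement is 26, and 26/41 = 63% of the fall. For B = 65, 75 and 95 the understatement is 5, 15 and 35. If the later result is also reported as >60, the change shown is 0 whatever happened: a true fall from 95 to 65 (-30) shows as 0.

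**Grade shift.** This step applies only if the converted value is graded. A converted 60 falls in the Grade 2 band, while a value above 60 is Grade 0 or 1.

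| Baseline as reported | Later value | Shift shown | True shift |
|---|---|---|---|
| >60 | 59, 45 or 31 | 2 to 2 | 0 or 1 to 2 |
| >60 | 25 | 2 to 3 | 0 or 1 to 3 |
| >60 | 14 | 2 to 4 | 0 or 1 to 4 |
| >90, Appendix 3 note applied | 65 | 0 to 1 | 0 to 1 |

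The hidden shifts are the moves into Grade 2, that is, falls that stay above 30. A fall to Grade 3 or 4 starts from the wrong grade but still shows as a shift and enters the Grade 3 and higher listing.

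**After the change.** With eGFR derived from creatinine, and assuming the derived values match the example, 86 to 45 gives -41 and a shift from Grade 1 to Grade 2. Graded from the reported text alone, >60 to 45 is a shift from Grade 0 or 1 to Grade 2.

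**Dipstick.** A 3+ protein is neither trace, 1+ nor 2+, and without hospitalization or dialysis it is not Grade 4. The same holds for 3+ glucose without hospitalization. Read literally, 2+ enters the Grade 3 and higher listing and 3+ does not.

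**The case against.** The strongest reply is that the conversion is confined to quantitative summaries and that grading is a separate step, so nothing in the SAP says that 60 would ever be graded. That is correct, and the grade-shift part is therefore conditional. The change-from-baseline part is not, because that summary is quantitative.

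The rule is also generic and never mentions eGFR, and no document says that any site reports >60. That stands too; the number of patients affected may be zero.

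A real renal decline has other ways to surface. Creatinine and BUN are graded and summarized separately, listings keep the reported text, and Protocol 7.2 requires clinically relevant abnormal results to be reported as adverse events. This limits the harm but does not make the eGFR tables right.

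Some stronger readings are tempting and go beyond the text:

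- A reader might infer that >90 becomes Grade 1. The Appendix 3 note, taken at face value, makes it Grade 0. Grade 1 follows only if conversion is run first and overrides that note.
- A reader might infer that normal kidneys are made to look impaired. A result of >60 does not show normal function, since the true grade may be 1.
- A reader might infer spurious improvements, such as >60 followed by 85 shown as +25. That needs a change of reporting format within one patient; a laboratory that censors at 60 would report >60 again.
- A reader might infer that 3+ protein is tabulated as normal. SAP 14.2.2 limits Grade 0 to normal or opposite-direction values, so 3+ is left ungraded. It would still appear in the qualitative summary by visit.

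**Conclusion.** The point holds in a limited form. For any patient with a baseline reported as >60, the SAP's rule understates a later measured fall in eGFR to 60 or below by the true baseline minus 60, which is 5 to 35 units for true baselines of 65 to 95. If converted values also feed grading, such a patient starts at Grade 2, a grade the reported result rules out, and falls that stay above 30 show no shift. Both effects rest on the assumption that some local laboratory reports >60. The documents are silent on this, so the affected share lies anywhere between 0 and 100%. The analysis is descriptive and other renal outputs exist, so this would not overturn the safety assessment. It is still a written rule that can put a wrong number into a primary-endpoint table, and it is easy to correct.

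The dipstick gap holds on the literal wording. Part of the Appendix 3 table is cut off in the available copy, so the full table should be checked for a medical-advisor flag on those rows.

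**What to change.** In SAP 14.2, derive eGFR centrally at every visit from serum creatinine, age and sex (and race if the version needs it), using the CKD-EPI equation that the protocol cites. Use the derived value for the change-from-baseline, shift and grading outputs. Creatinine is collected at every visit, all patients are male, and SAP 10 already reports age and race. This also removes differences between sites in the equation used.

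Where creatinine is missing, grade from the reported text: >90 is Grade 0 and >60 is not worse than Grade 1. Do not use the converted value for change from baseline.

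In Appendix 3, change the Grade 3 analysis category for dipstick protein and glucose from 2+ to 2+ or more. Footnote that this extends the wording of the scale in Protocol 11.2.

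The cost is one derived variable, a few lines of SAP text and minor programming. No new data are needed.
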